7.2. Multiplicity Adjustment

The primary and the ranked secondary efficacy analyses will be performed at an overall alpha level of 0.05 (two-sided) comparing relugolix + E2/NETA (Group A) with placebo (Group C). A test will be deemed statistically significant if the two-sided p-value rounded to four decimal places is < 0.05. A gate-keeping testing procedure will be applied to maintain the family-wise type I error rate for the testing of primary and ranked secondary endpoints (see Section 7.4.1 for details).

Comparative statistics (p-values, 95% CIs for differences) will be provided for the treatment comparison of relugolix + E2/NETA with placebo for all other secondary efficacy endpoints. A treatment comparison of relugolix + delayed E2/NETA (Group B) with placebo will be performed only for the primary efficacy endpoint. There will be no statistical testing for treatment differences between the relugolix groups (Group A versus Group B) for any efficacy endpoints. The relugolix + E2/NETA group and relugolix + delayed E2/NETA group will be compared for the following safety endpoints: percent change from Baseline to Week 12 in BMD and incidence of vasomotor symptoms by 12 weeks (see Section 9.3.5 and Section 9.1.7, respectively). The above comparative analyses are not part of the gate-keeping testing procedure for label claims. p-values for primary and key secondary endpoints were adjusted for multiplicity. All other p-values are provided at a nominal level of 0.05.

7.3. Primary Efficacy Endpoint

The primary efficacy endpoint of the study is the proportion of women who achieve an MBL volume of < 80 mL AND at least a 50% reduction from Baseline in MBL volume over the last 35 days of treatment as measured by the alkaline hematin method. The primary endpoint will be referred to as responder rate and derived on the basis of the total MBL volume measured at the Week 24/EOT visit window taking into consideration the patient's compliance with return of feminine products and completion of the eDiary (see Section 7.3.2 and Section 7.3.4 for details).

7.3.1. Primary Efficacy Analysis

The following primary hypothesis for the primary efficacy endpoint will be tested:

Null hypothesis $H_0: \pi_R \leq \pi_P$ versus Alternative hypothesis $H_{a1}: \pi_R > \pi_P$

where π_R and π_P are the responder rates at Week 24/EOT for relugolix + E2/NETA (Group A) and placebo (Group C), respectively.

The treatment comparison between the relugolix + E2/NETA and the placebo will be analyzed using a Cochran-Mantel-Haenszel test statistic for proportions stratified by the Baseline mean MBL volume using the alkaline hematin method (< 225 mL versus ≥ 225 mL) and geographic region (North America versus Rest of World). The difference in responder rates between the relugolix + E2/NETA and placebo and its two-sided 95% CI will be estimated using stratum-adjusted Mantel-Haenszel proportions. The unadjusted responder rates and the difference in responder rates between the relugolix + E2/NETA and placebo groups and the corresponding two-sided 95% CI also will be provided. The study will be considered positive if the treatment effect for the primary endpoint is statistically significant with two-sided p-value < 0.05 .

[figure not shown]
For the primary analysis, primary endpoint will incorporate the missing data handling rules described in Section [7.3.5](#).

7.3.2. Data Sources Supporting Derivation of Responder Status

The data sources that will be used to support derivation of responder status, the primary endpoint, are depicted in [Figure 2](#) below. They include:

- Menstrual blood loss volume determined by the alkaline hematin method;
- Daily patient report of bleeding (yes/no) and use of feminine product (yes/no) captured in the eDiary;
- The status of feminine product (FP) collection return (yes/no) recorded on the eCRF page at each visit with specific reasons captured when no product collection was returned.

The total MBL volume is reported from the analysis of FP returned for each collection interval. An inventory of days (with dates) for which FP was collected and returned is also available. This inventory is aligned with patients' reports of bleeding and FP use in the eDiary. The status of FP collection return, and specifically the reason for non-return of FP reported on the Feminine Product Collection eCFR page is used to support derivation of responder status (see Section [7.3.5](#) for details).

Figure 2: Data Sources Supporting Derivation of Primary Endpoint

Abbreviations: CRF = case report form.

7.3.3. Definitions Related to Menstrual Blood Loss

Menstrual Blood Loss Volume

All returned feminine products (validated, validated but unauthorized, or unvalidated products) collected at each visit will be analyzed by the alkaline hematin method to obtain the MBL volume. The MBL volume measured over the Week 24/EOT feminine product collection interval (up to 35 days prior to the last dose of treatment) will be used for analysis of the primary efficacy endpoint (see details below). The vendor, KCAS, reports when unauthorized feminine products (products not dispensed for use in the trial) have been returned. KCAS also reports whether the unauthorized products have previously been validated for their analysis. The report details MBL volumes for authorized, unauthorized but validated, and unauthorized and unvalidated products.

Validated Menstrual Blood Loss Volume

All returned feminine products collected at each visit, with the exception of unvalidated products, will be assessed by the alkaline hematin method to obtain the validated MBL volume. The validated MBL volume is derived from assessments of all returned validated feminine products (including validated and validated but unauthorized products) and will be used for sensitivity analysis.

Baseline Menstrual Blood Loss Volume

Baseline MBL volume is defined as the average MBL volume from the one or two consecutive screening menstrual cycles used to meet the inclusion criteria prior to the date of the first dose of study drug as assessed by the alkaline hematin method as follows:

For patients with MBL volume \geq 160 mL during the screening period, the Baseline MBL volume is the last measurement collected before the first administration of study drug.

If the MBL volume is $<$ 160 mL, the Baseline MBL volume is defined as the average of the MBL volume from the two screening menstrual cycles used to meet the inclusion criteria prior to the date of the first dose of study drug as assessed by the alkaline hematin method (see Figure 4-2 of the study protocol for details).

Week 24/EOT Feminine Product Collection Interval

To ensure collection of all feminine products used during that menstrual cycle, an interval of up to 35 days for measurement of the primary endpoint was selected to accommodate women who continue to have cyclic bleeding on study treatment and whose natural cycle was at the upper end of the normal cycle duration range. This method is consistent with that used during screening for collection of feminine products. Specifically, the feminine product collection interval at Week 24/EOT is driven by types of bleeding patterns experienced by the patients, as described below:

- For patients who continue to have cyclic bleeding, the length of the interval depends on the duration of the patient's natural cycle; this is consistent with the way the Baseline MBL volume was determined (eg, the interval ranging from approximately 21 to 35 days);
- Patients who report irregular, non-cyclic bleeding are instructed to collect and return all feminine product used between study visits, up to 35 days, as per the schedule of events;
- For patients who report amenorrhea on the feminine production collection eCRF page, an interval of last 35 days of treatment will be reviewed to ensure that reported amenorrhea is not due to incomplete collection.

For patients who are in the midst of an episode of cyclic bleeding at the time of the Week 24/EOT visit, the visit window may be extended up to 7 days after the last dose of study drug to ensure patients return all used feminine products over that bleeding episode.

Per protocol, all used feminine products are to be collected at each visit and returned for analysis using the alkaline hematin method. For patients who continue to have menstrual bleeding, study visits are timed such that the feminine products used in the entire menstrual bleeding cycle are collected in one container provided at each visit.

MBL Volume at Week 24/EOT

MBL volume at Week 24/EOT is defined as the MBL volume obtained from the feminine product returned over the Week 24/EOT feminine product collection interval, as described above. The MBL volume at Week 24/EOT will be used to derive the primary efficacy endpoint.

If a patient did not return feminine product over the last 35 days of treatment and reported amenorrhea on the feminine product return eCRF page, she will be considered as amenorrhoeic and her MBL volume will be assigned as 0 mL.

Feminine Product Return Rate at Week 24/EOT

To quantify degree of compliance with feminine product collection, the FPRR will be calculated based on the inventory of feminine product returned by day (dates) summarized on the Feminine Product Collection eCFR page (provided by the vendor, KCAS) and responses to the eDiary Question 4 regarding bleeding experience and Question 5 regarding the use of feminine product obtained for the corresponding eDiary window (see [Table 5](#)). Specifically:

- For those who returned feminine product at Week 24/EOT, the FPRR was calculated as the observed number of days with returned feminine products (based on the inventory of FP received by KCAS) divided by the expected number of days with bleeding and use of product as reported on the eDiary within the Week 24/EOT feminine product collection interval (as defined above).
- For those who did not return any feminine products:
 - If the reason was amenorrhea reported on the eCRF or if spotting/negligible bleeding was reported on the eCRF and confirmed by eDiary over the Week 24/EOT visit window, their FPRR will be set to 100% because the lack of menstruation obviates the need for feminine product collection.
 - Otherwise if the reason is any other, their FPRR was set to 0.

$$\text{FPRR} = \frac{\text{observed (No. of days with returned FP [per KCAS])}}{\text{expected (No. of days reported bleeding and use of FP [per eDiary])}} \times 100$$

Return of feminine products will be summarized in the CSR for Week 24/EOT visit.

7.3.4. Definition of Responder at Week 24/EOT

A responder at Week 24/EOT is defined as a patient who satisfies both the following:

- Had MBL volume of < 80 mL at Week 24/EOT;
- Had at least a 50% reduction from Baseline in MBL volume at Week 24/EOT.

The reduction from Baseline in MBL volume at Week 24/EOT will be calculated as the absolute change at Week 24/EOT in MBL volume from the Baseline MBL volume divided by the Baseline MBL volume.

Responder status at Week 24/EOT will be assessed based on the reported MBL volume at Week 24/EOT, in conjunction with treatment duration, compliance with feminine product collection, and compliance with eDiary entry over the same visit window (see Section [7.3.5](#) for details).

7.3.5. Derivation of Responder Status at Week 24/EOT and Missing Data Handling Rules

For the evaluation of primary endpoint, missing data handling rules will be implemented for deriving responder status at Week 24/EOT as described below. The following elements will be checked: duration of treatment exposure; compliance with feminine product collection against the eDiary, as measured by FP RR; compliance with eDiary entry, defined as the proportion of eDiary entry days over the length (days) of FP collection interval for Week 24/EOT visit; and reasons for no FP collection (as displayed in [Table 7](#)).

Patients with < 4 weeks of treatment who withdraw from the study prematurely due to lack of efficacy or withdraw from the study prematurely to undergo surgical intervention for uterine fibroids will be considered as non-responders.

All other patients will have their responder status determined as follows:

- For patients with a FP RR of 100%, responder status will be determined based on the observed MBL volume;
- For patients who had incomplete feminine product collection, with a FP RR of < 100%, responder status will be derived based on either imputed or observed MBL volume;
 - Those with an MBL volume \geq 80 mL or < 50% reduction from Baseline will be considered as non-responders;
 - Those with an MBL volume < 80 mL and \geq 50% reduction from Baseline will be imputed for partial or complete missing MBL volume (see Section [7.3.6](#) for details).
- For patients who did not return a feminine product collection, responder status will be determined depending on the reason reported on the Feminine Product Collection eCRF:
 - If the reason is reported as Amenorrhea, the last 35 days of treatment will be used to derive responder status:
 - If the Week 24/EOT interval was 35 days, then she will be considered as a responder;
 - If the Week 24/EOT interval was <35 days, the following supportive information will be used to derive responder status:
 - If a patient reported amenorrhea at the visit prior to Week 24/EOT, she will be defined as a responder;
 - If a patient did not report amenorrhea at the visit prior to Week 24/EOT, eDiary data from the prior visit interval will be reviewed to confirm whether the patient was amenorrheic for a total of 35 days.

- If the eDiary from the previous interval confirms amenorrhea, then the patient will be considered as a responder;
- Otherwise, MBL volume will be imputed.

- If the reason is Other and the specification describes spotting or negligible bleeding, responder status will be defined as follows:

- The patient will be considered as a responder if it is supported by the eDiary data: the eDiary entry rate must exceed 70% and the patient must have reported no more than 5 total days of bleeding with product use and no more than 3 consecutive bleeding with product use over the collection interval.
- If the eDiary entries did not confirm spotting or negligible bleeding, but the patient had at least 8 weeks of MBL volume data prior to the Week 24/EOT visit, her missing MBL volume will be imputed to determine responder status. Eight weeks of MBL volume data represents a reasonable minimum length of observation to justify imputation of the remaining data in assessing the effects of hormonal therapy.
- Otherwise if the patient had < 8 weeks of MBL volume data, she will be considered as a non-responder;

- If the reason is any Other, the responder status will be derived as follows:

- If the patient had at least 8 weeks of MBL volume data prior to the Week 24/EOT visit, her missing MBL volume will be imputed and her responder status will be based on the imputed MBL volume.
- If the patient had < 8 weeks of MBL volume data, she will be considered as a non-responder.

Table 7: Derivation of Responder Status at Week 24/EOT and Missing Data Handling Rules – for Primary Analysis

Treatment Exposure	FP Collection (FPRR)	Observed MBL Volume	Reason for No FP Collection	Responder Status
< 4 weeks	N/A	N/A	N/A	Imputed as non-responder
≥ 4 weeks	100% FP Compliance	N/A	N/A	Based on the observed MBL volume
	<100% FP Compliance	MBL volume ≥ 80 mL or <50% reduction from Baseline	N/A	Imputed as non-responder based on the observed MBL volume
		MBL volume < 80 mL and ≥ 50% reduction from Baseline	N/A	Based on the imputed MBL volume
	No FP Collection	N/A	Reported “Amenorrhea”	Imputed as responder
			Reported “Spotting or negligible bleeding” and confirmed by eDiary ^a	Imputed as responder
			Reported “Spotting or negligible bleeding” although not confirmed by eDiary or any other reason, had at least 8 weeks of MBL volume data	Based on the imputed MBL volume
			The entries in the eDiary did not verify “Spotting or negligible bleeding” or any other reason and if had < 8 weeks of MBL volume data	Imputed as non-responders

Abbreviations: eDiary, electronic diary; FP, feminine product; EOT, end of treatment; MBL, menstrual blood loss; N/A, not available.

^a Defined as those patients who meet the following criteria: eDiary entry rate > 70% and no more than 3 consecutive days and no more than 5 days of bleeding/spotting and use of feminine product reported on the eDiary over the Week 24/EOT visit window (see [Table 5](#)).

7.3.6. Mixed-Effects Model for Imputing Missing or Partially Missing MBL Volume at Week 24/EOT

For the primary analysis, patients with missing MBL volumes at Week 24/EOT will be identified per missing data handling rules as described above. For imputing missing data for the primary analysis, a mixed-effects model approach will be used, as the mixed-effects approach may better describe the effects of a hormonal treatment (such as suppression of the hypothalamic-pituitary-ovarian axis by GnRH antagonists).

Specifically, a mixed-effects model with repeated measures of MBL volumes at multiple time points (Weeks 4, 8, 12, 16, 20 and 24) will be fitted to predict percent change in MBL volume from Baseline (as a dependent variable) through the fixed-effects associated with covariates (ie, stratification factors of Baseline MBL volume and geographic region, visit, treatment, and visit by treatment interaction) and random effects (from the individual patients). In this model, an unstructured variance-covariance matrix is assumed for each patient.

See sample SAS codes below for illustration where PCHG_MBL is percent change in MBL volume from Baseline as a dependent variable, PID is patient identification number, BMBL is a randomization stratification factor (Baseline MBL < 225 vs \geq 225), REGION is a randomization stratification factor (North America vs Rest of World), TRT is treatment group (relugolix + E2/NETA or Placebo), VISIT is visit time point (4, 8, 12, 16, 20, and 24 weeks) and TRT*VISIT is the visit by treatment interaction. The specification of type=UN implements unstructured variance-covariance matrix for an individual patient with multiple measures of MBL volumes.

```
proc mixed data=MBL_dataset method=REML covtest;
  class PID BMBL REGION TRT VISIT;
  model PCHG_MBL= BMBL REGION VISIT TRT VISIT*TRT/s outp=ufmi_mixed_p
  covb;
  repeated VISIT /type=UN subject=PID r;
  lsmeans TRT/diff;
  ods output SolutionF=mixparms CovB=mixcovb;
```

Applying this model over the observed longitudinal MBL volume data, the fixed-effects will be estimated and relationship of percent change in MBL volume from Baseline with the covariates will be characterized by the fitted model. From the fitted model, the percent change in MBL volume (whether missing or not) will be predicted for each patient at each visit and in a particular stratum. The imputed MBL volume will be obtained by first multiplying the imputed percent change with the individual patient's Baseline MBL volume to the difference, and then adding the Baseline BML volume to the difference.

The main reason for using percent change in MBL volume over reported MBL volume as a dependent variable in the mixed-effects model is that the percent change is part of the derivation of the primary endpoint. Secondly, the percent change is a normalized value adjusted for the Baseline value and less influenced by Baseline MBL volume, and therefore it is a better metric to describe the relationship of MBL volume reduction with hormonal treatment and to impute the missing volumes in a more robust fashion.

Statistical Analysis Plan
Amendment 1: Effective June 14, 2019

MVT-601-3001 and 3002

Since the purpose of using a mixed-effects model is imputing the missing MBL volumes identified at Week 24/EOT, the predicted MBL volumes at the corresponding Week 24/EOT visit will be used to determine responder status. For patients without the need for imputation, their responder status will be derived according to the algorithms laid out in [Table 7](#). This imputation approach is consistent with the definition of responder at Week 24/EOT for the primary analysis.

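### Section 7.3.5 and Tables 7 and 8 disagree on who is a primary-endpoint responder, and imputed women enter the primary test as if observed

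*SAP*

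**What the plan says.** **Early withdrawal.** The text of Section 7.3.5 makes non-responders of "Patients with < 4 weeks of treatment who withdraw from the study prematurely due to lack of efficacy or withdraw from the study prematurely" for fibroid surgery, and sends all remaining women to the collection rules with no condition on exposure. In Table 7, and again in Table 8, the row for under 4 weeks of exposure reads "Imputed as non-responder" with every other column marked N/A.

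**Reported amenorrhea with no collection.** If the Week 24/EOT interval is shorter than 35 days, the text asks for amenorrhea at the prior visit or eDiary confirmation. Failing both, "Otherwise, MBL volume will be imputed". The amenorrhea row of Tables 7 and 8 says "Imputed as responder" without condition. Section 7.3.3 points both ways. It says the last 35 days "will be reviewed to ensure that reported amenorrhea is not due to incomplete collection", yet for a woman whose eCRF reports amenorrhea it sets the product return rate (FPRR) without that check: "their FPRR will be set to 100% because the lack of menstruation obviates the need for feminine product collection".

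**Which source governs.** Section 7.3.1 says the "primary endpoint will incorporate the missing data handling rules described in Section" 7.3.5, which contains both the text and Table 7. Section 7.3.6 refers women who need no imputation to Table 7.

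**Imputation.** Section 7.3.6 fits a repeated-measures model to percent change in MBL volume ("In this model, an unstructured variance-covariance matrix is assumed for each patient"), takes the predicted Week 24/EOT volume and sets responder status from it. Section 7.3.1 then applies the ordinary CMH test and Mantel-Haenszel interval. Multiple imputation appears only in Sensitivity Analysis 6.

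**The concern.** The primary endpoint should have one derivation. Here two programmers working in good faith from the same section could classify the same woman differently. Section 7.4.2 reuses these rules for time to response and for responder rate by visit, so the ambiguity spreads to those endpoints.

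The imputation step is a separate problem. A single predicted mean per woman, once cut at the thresholds, is treated as an observed outcome, so the standard error has no term for not knowing the value. Predicted means also vary less than real volumes. Cutting them at a fixed threshold pushes an arm whose true rate is below 50% further down, and one above 50% further up. At the planned rates of 25% and 55%, both movements favour the active arm. What is at stake is the primary estimate, its interval and the reproducibility of responder status.

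**Working it through.** **Inputs from the SAP (Section 2.2.1):** two-sided 0.05, 130 women per arm, 25% placebo response, 30-point difference, about 20% dropout. The imputed share and the correlation between visits are not given and are varied below.

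**1. The plan's own figure.** Evaluable women: 130 × 0.8 = 104 per arm. With pooled rate 0.40, z = [0.30 − 1.96 × √(2 × 0.40 × 0.60/104)] / √[(0.55 × 0.45 + 0.25 × 0.75)/104] = (0.300 − 0.133)/0.0647 = 2.58, so power is 99.5%. The stated figure of at least 99% reproduces.

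**2. Early withdrawal: both readings conflict with the tables.**
- *One group.* Only women with under 4 weeks who left for lack of efficacy or surgery are non-responders. The tables make all women with under 4 weeks non-responders.
- *Separate groups.* Women with 4 weeks or more who left for one of those reasons are non-responders too. The tables have no such row and put them through the ordinary rules, where they can be responders.

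One woman is 1/130 = 0.8 points. If dropout is spread evenly over 24 weeks (assumption), 130 × 0.20 × 4/24 = 4.3 women per arm stop before Week 4, at most 3.3 points on the first reading. Another 130 × 0.20 × 20/24 = 21.7 stop later. If 10–30% of these leave for lack of efficacy or surgery (assumption), that is 2.2–6.5 women, at most 1.7–5.0 points on the second reading. Only women whom the algorithm would otherwise call responders change status.

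**3. Amenorrhea.** Target days 141 and 169 are 28 days apart, so about 35 − 28 = 7 earlier days need confirmation. Status differs between text and table only when the prediction is a non-response. The number of women cannot be derived.

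**4. Thresholding, closed form.** Assume a normal scale, one cut-off and five earlier visits with equal correlation r. Then R² = 5r²/(1 + 4r), and the rate called responder among imputed women is Φ(Φ⁻¹(p)/√R²).

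| r | R² | Placebo called (true 25%) | Active called (true 55%) | Added to difference at 10% imputed |
|---|---|---|---|---|
| 0.3 | 0.205 | 7% | 61% | 2.4 points |
| 0.5 | 0.417 | 15% | 58% | 1.3 points |
| 0.7 | 0.645 | 20% | 56% | 0.6 points |

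**5. Simulation.** 108 scenarios of 2,000 runs each (Monte Carlo error about 0.5 points), with 130 women per arm and six visits. MBL ratio to Baseline was log-normal (log-SD 1), or percent change was normal (SD 45, floored at 0 mL); volumes under 5 mL were set to 0. Correlation was 0.3, 0.5 or 0.7. Women were flagged either by no collection, missing at random, or by partial return measuring 30–95% of the true volume and imputed only if both criteria appeared to be met. The analysis was the stratified CMH test and Mantel-Haenszel difference. Shift and coverage are at 55% versus 25%; null rejection is at 25% or 40% in both arms. The comparator took 50 draws from the same percent-change model, with parameter and residual uncertainty, combined by Rubin's rules.

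| Flagged | Shift, single (points) | Coverage, single | Null rejection, single | Coverage, multiple | Null rejection, multiple |
|---|---|---|---|---|---|
| 5% | 0.0 to +0.8 | 92.1–94.7% | 4.8–6.8% | 94.2–95.9% | 4.2–6.6% |
| 10% | 0.0 to +1.5 | 91.2–94.5% | 4.2–8.5% | 94.5–96.4% | 3.7–5.9% |
| 20% | 0.0 to +3.0 | 86.2–93.7% | 5.9–10.0% | 94.8–96.7% | 2.1–5.2% |

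One cell as an example (20% flagged, r = 0.3, normal percent change, no collection): the reported SE is 5.46 points against an actual SD of 6.57, a ratio of 0.83.

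A second simulation, with 1,000 runs per cell, normal percent change and correlation 0.5 between Week 24 and earlier visits, gave a difference of 31.7 points with 92.1% coverage at 10% imputed, and 33.2 points with 87.5% at 20%. Multiple imputation of the same data gave 29.9 points with 96.5%, and 29.5 points with 96.2%. With correlation 0.8 and 5% imputed, the single prediction gave 30.1 points and 95.1%, so the effect can be negligible.

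**The case against.** - **Sensitivity analyses cover part of this.** Analysis 3 makes every stop in the first 4 weeks a non-response, and also stops up to Week 12 for reasons that include lack of efficacy and surgery. Analysis 2 drops imputation for partial returns. Analysis 6 uses 100 imputations with Rubin's rules. That is true, but none of them changes the primary estimate, interval or p-value. Table 8 governs Analysis 2 only; it matters here because it repeats the two disputed rows.
- **Table 7 may be only a summary.** Section 7.3.6 applies it to women without need of imputation, so a woman the text sends to imputation could be read as outside it. But whether she needs imputation is exactly where text and table differ, so this gives no working order of precedence.
- **The rule-conflict figures are ceilings.** This stands. Women with no collection for some other reason and under 8 weeks of MBL data are non-responders under both versions. Women leaving for lack of efficacy are unlikely to meet both criteria.
- **Dropout is not imputation, and 20% flagged may be high.** This also stands. Women who stop early are scored on their own end-of-treatment data, and several no-collection cases are settled by rule. The worst figures all come from the 20% row.
- **The closed form exceeds the simulation** (2.4 against at most 1.5 points at 10%). The closed form uses one normal cut-off and known coefficients. The simulation has both criteria, a floor at zero, estimated coefficients and a partial-return mechanism, and is the better guide to size.
- **The remedy has a bias of its own** when volumes are log-normal. This is correct, and it is counted as a cost of the change.

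**Conclusion.** The concern holds. Text and tables contradict each other on early withdrawal under either reading of the sentence, and on unconfirmed amenorrhea, and the SAP gives no rule of precedence. Few women are likely to be affected, each worth 0.8 points in her arm.

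The omission of imputation variance follows from the method itself. Its size does not: it depends on the imputed share and on how well earlier visits predict Week 24, neither of which the SAP gives. With 5–10% flagged, the difference moves by 0.0 to +1.5 points and coverage is 91.2–94.7%. With 20% flagged the figures are up to +3.0 points and as low as 86.2%. In every scenario at the planned rates, the shift was zero or toward the active arm. With few imputed women or strong correlation the effect is slight. At 99.5% design power, the significance conclusion at the planned effect does not depend on this. The point should be fixed, but it does not undermine the trial.

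**What to change.** Before unblinding:

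1. **One rule per cell.** State the same rule in the Section 7.3.5 text, Table 7 and Table 8. Carry the 35-day confirmation of Sections 7.3.3 and 7.3.5 into the amenorrhea row and the FPRR definition. State one early-withdrawal rule, as the sponsor intends it, covering both exposure under 4 weeks and later withdrawal for lack of efficacy or surgery. The passages need reconciling; which rule to adopt is the sponsor's decision.
2. **Proper draws in the primary analysis.** For women sent to imputation, replace the single prediction with multiple random draws from the percent-change model already in Section 7.3.6, including parameter and residual uncertainty. Apply both thresholds to each draw and combine the results by Rubin's rules for the estimate, interval and test. Keep the single prediction and Sensitivity Analysis 6 as sensitivity analyses.

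**Cost.** Wording in the text, two tables and one definition, plus a little programming. In the first simulation, power stayed at or above 99.7%. At 10% flagged, the interval half-width rose from 10.8–11.0 to 11.2–11.6 points. With log-normal volumes, the difference shrank by 0.8–1.1 points at 10% flagged and 1.6–2.1 at 20%. With normal percent change it moved by −0.5 to +0.7 points at most. Null rejection fell as low as 2.1% at 20% flagged, so where the replacement errs there it is on the conservative side.
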